Research Proposal
[name], DO
WSU-SOM, OBGYN, PGY-2

Title

- Postpartum management of gestational hypertensive disorders using furosemide: A randomized controlled trial

Investigators

- Primary Investigator
 - [name], DO, PGY-2, Capt, USAF
 - [contact]
 - [contact]
- Investigators
 - [name], MFM subspecialist at MFMUG
 - [contact]
 - [contact]
 - [name], WSU-SOM Teaching Faculty
 - [contact]
 - [contact]

Summary

- The main purpose of this study is to learn if incorporating a loop diuretic such as furosemide along with labetalol in the routine management of postpartum gestational hypertensive disorders could lower the need for additional anti-hypertensive agents to control blood pressures, improve blood pressures (as measured by systolic blood pressure, diastolic blood pressure and mean arterial blood pressures), shorten hospital stays and decrease readmissions for patients with gestational hypertensive disorders.
- Based on a study by Veena et al¹, there is reason to believe that the addition of furosemide to other anti-hypertensives may help decrease the need to add or increase the dose of medication to control blood pressures. There may be potential to shorten hospital stays and decrease readmissions, as well. Collecting data will be done using a prospective, randomized 1:1 controlled study assigning postpartum patients with a gestational hypertensive diagnosis to either labetalol alone or labetalol plus furosemide.
- Based on an estimated 8% need for increase in anti-hypertensive medication in the furosemide group and a 26% need in the standard treatment arm, to achieve 90% power

with a 2-sided alpha of 0.05, we calculate 96 patients per group. Analysis will be via Chi-square or Fisher's exact test for categorical variables. Student T-Test and Mann Whitney U tests will be utilized to compare continuous variables. Randomization will be performed using REDCap.

- The study will be performed in the postpartum wing of Miami Valley Hospital Main Campus and would recruit patients who have consented to participate in the study with enrollees coming from the OB Staff population.

Background and Literature Review

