- With the construct of the study, we would be keeping costs low by utilizing already established resources and practices (blood pressure cuffs, nurses, routine one week blood pressure checks) while only adding on the unit cost of furosemide and basic metabolic panels.
- If treatment with labetalol and furosemide is found to be useful, it would be not only a very inexpensive, cost effective way of improving patient outcomes and possibly decreasing lengths of stay, but possibly improvement in global practice in places that are lacking in resources privy to first world countries.

Methods

- A prospective randomized 1:1 controlled trial including postpartum women with gestational hypertension or preeclampsia
 - Inclusion criteria: Age 18-45, Postpartum: 24-72 hours after delivery, no contraindications to the study medications
 - Exclusion criteria: chronic hypertension diagnosis, creatinine levels above 1.5 $\mu\text{m}/\text{L}$, unable to give consent
- One arm receiving 200mg labetalol BID alone on Day#1 or at least 24 hours after magnesium sulfate, if given
- One arm receiving 200mg labetalol BID and a five day course of furosemide 20mg QD on Day#1 or 24 hours after magnesium sulfate
 - The 20 mg dose is the standard dose for furosemide in this population.
- Titrate labetalol to maintain blood pressures below 150 SBP and/or 100 DBP per ACOG recommendations.⁷
 - In the event of persistently elevated blood pressures, labetalol will be increased to 400mg BID and escalated to 600mg BID and finally 800mg BID as indicated
- Measurement of blood pressure every four hours until patient discharge
- Daily BMPs to assess for electrolyte abnormalities
- Measurement of urine output every 12 hours until discharge
- Demographics
 - Age (18-24, 25-34, 35-44, 45-51)
 - Nulliparous (yes, no)
 - BMI (underweight, normal, overweight, obese)

- Race (Caucasian, African American, Asian, Hispanic, Other)
- Diabetes (yes, no)
- Multiple gestation (yes, no)
- Preterm delivery (yes, no)
 - Gestational age at delivery
- Cesarean delivery (yes, no)
- IVF pregnancy (yes, no)
- History of previous gestational hypertension/pre-eclampsia (yes, no)
- Systemic lupus erythematosus (yes, no)
- Renal disease (yes, no)
- Outcome variables
 - Need for additional antihypertensive medication (yes, no)
 - Labetalol 400mg BID
 - Labetalol 600mg BID
 - Labetalol 800mg BID
 - Highest systolic blood pressure (mmHg)
 - Highest diastolic blood pressure (mmHg)
 - Mean arterial blood pressure

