 - Daily urine output (mL)
 - Length of postpartum stay (days)
 - Readmission for hypertension (yes, no)
 - Breastfeeding at 1 week postpartum (yes, no)
- The study duration is the length of the hospital stay plus 1 week postpartum blood pressure check.
- The research will be analyzed and interpreted by the research team conducting the study.
- Potential difficulties and limitations include compliance concerns of mandatory one week blood pressure follow up appointment.
- The unit cost of one tablet of labetalol 200mg and furosemide 40mg is currently \$0.32 and \$1.23, respectively.^{8,9}
- The study would use already readily available automated blood pressure cuff machines on the postpartum wing.

Safety Monitoring

Monitoring of blood pressures will be performed every four hours while on the maternity postpartum floor. If the patient is found to be above 160 systolic or 110 diastolic, it will be rechecked in fifteen minutes. If still elevated, then escalation of blood pressure medicine will be done. The healthcare provider will ask the patient if they are exhibiting any signs of profound hypertension and/or hypokalemia including headache, vision changes, dizziness, lightheadedness, weakness, fatigue, muscle cramping, or heart palpitations. If any of these are identified, a physician will be notified and will assess the patient.

Patients will be instructed to let their doctor/nurses know if they are experiencing known side effects of Lasix that include new onset weakness, fatigue, muscle cramping, dizziness or

heart palpitations. If a patient has severe symptoms after discharge, they will be instructed to call the afterhours phone number on the consent form.

If a patient has signs of hypokalemia, we will test lab values for potassium (K+) levels (Complete metabolic panel). We will continue administering Lasix if the potassium result is between 3.0 and 3.4 $\mu\text{m}/\text{L}$ and we will administer 20 mEq KDur BID. If it is less than 3.0 $\mu\text{m}/\text{L}$ we will stop using Lasix.

References

- 1) Veena, P., et al. “Furosemide in Postpartum Management of Severe Preeclampsia: A Randomized Controlled Trial.” *Hypertension in Pregnancy*, vol. 36, no. 1, 2016, pp. 84–89., doi:10.1080/10641955.2016.1239735.

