Postpartum management of gestational hypertensive disorders using furosemide: A randomized controlled trial

Statistical Analysis Plan

Version Jan 9, 2020

[name]; [name], DO; [name]

The statistical analysis plan is based on the objectives of the study as follows:

Main Question: Does the use of furosemide plus labetalol improve blood pressures in the postpartum period of patients with gestational hypertensive disorders versus labetalol alone?

Primary:

Does the addition of a 5-day course of furosemide to labetalol avoid the escalation of anti-hypertensive therapy to control blood pressures.

Analysis plan: Randomization groups (labetalol + furosemide vs labetalol alone) will be compared using a Fisher's Exact test for number of patients who have had an escalation of labetalol dose at any time during their hospital stay.

Secondary:

Does the addition of furosemide to labetalol in postpartum hypertension:

1. Improve of systolic blood pressure, diastolic blood pressure and mean arterial pressure.

Analysis plan: Randomization groups will be compared on daily means for each outcome by repeated measures ANOVA to determine difference in outcomes across time (Day 0/Baseline, Day 1, and Day 2). One repeated measures ANOVA will be performed for each of the three outcomes (systolic blood pressure, diastolic blood pressure, and mean arterial pressure).

2. Shortened hospital stay

Analysis plan: Randomization groups will be compared on hospital length of stay using a Student T-test.

3. Affect breastfeeding status at 1 week postpartum visit in mothers planning to breastfeed.

Analysis plan: Randomization groups will be compared on breastfeeding status at the postpartum visit using a Fisher's Exact test.

4. Decrease readmission for postpartum hypertensive disorders.

Analysis plan: Randomization groups will be compared on the number of participants who were hospitalized after discharge using a Fisher's Exact test.

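### The SAP's blood pressure ANOVA uses Day 0/Baseline as an outcome level rather than adjusting for it, and names neither the treatment test nor a rule for women discharged before Day 2

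*SAP*

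**What the plan says.** The SAP, under Secondary objective 1, states "Randomization groups will be compared on daily means for each outcome by repeated measures ANOVA". The purpose given is a "repeated measures ANOVA to determine difference in outcomes across time (Day 0/Baseline, Day 1, and Day 2". It adds that "One repeated measures ANOVA will be performed for each of the three outcomes", so systolic, diastolic and mean arterial pressure share the same specification.

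The protocol Methods start the control arm as "One arm receiving 200mg labetalol BID alone on Day#1 or at least 24 hours after magnesium sulfate, if given" and the other arm adds a "five day course of furosemide 20mg QD on Day#1 or 24 hours after magnesium sulfate". Blood pressure data in hospital end at discharge: "Measurement of blood pressure every four hours until patient discharge". For continuous outcomes the protocol Summary says only that "Student T-Test and Mann Whitney U tests will be utilized to compare continuous variables".

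Neither document names a baseline covariate, defines Day 0, identifies the ANOVA term or contrast that tests treatment, or gives a rule for missing readings after discharge.

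**The concern.** There are three linked gaps.

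1. **Baseline.** Day 0 is labelled as baseline and treatment starts on Day#1, so it reads as pre-treatment. It then carries information about each woman's later pressure but nothing about the treatment effect. A group-by-time test in effect subtracts it. Adjustment uses it at its optimal weight.
2. **Treatment term.** The group-by-time interaction is the natural reading, but the group main effect is not excluded. The main effect averages a zero Day 0 difference with the Day 1 and Day 2 differences.
3. **Early discharge.** Women who leave before Day 2 have no Day 2 mean. A classical repeated measures ANOVA drops them entirely, while a mixed model keeps their earlier days. A shorter stay is itself a hypothesised benefit, so this loss could differ by arm.

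Blood pressure is the trial's stated main question and its first secondary objective. As written, the result depends on choices that could be made after the data are seen, and the most natural version makes less use of the readings than it could.

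**Working it through.** **Inputs.** From the documents: 96 per arm, 1:1 allocation, two-sided 5%, three time levels. The 96 comes from the primary outcome (8% against 26%, 90% power). Exact two-sided Fisher power is 89.6% at 94 per arm and 90.3% at 96, so 96 reproduces. No figure is stated for blood pressure. Assumed: effect d = 1/3 SD (for example 4 mmHg with SD 12), and equal correlation ρ between days.

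**Group-by-time test (2 and 380 df).** With day effects v = (0, d1, d2), the noncentrality is λ = (n/2) × Σ(v − v̄)² / (1 − ρ).

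**Baseline-adjusted joint test of arm on Days 1 and 2 (2 and 188 df).** With x = (d1, d2), λ = (n/2) × x′S⁻¹x. S is the covariance of Days 1 and 2 given Day 0: variance 1 − ρ², covariance ρ − ρ².

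**Worked case: constant effect, ρ = 0.5.**
- Group-by-time: Σ(v − v̄)² = (2/3)(1/9) = 0.0741, so λ = 48 × 0.0741 / 0.5 = 7.11 and power is 65.9%.
- Adjusted: x′S⁻¹x = 2d²/(1 + ρ − 2ρ²) = 0.2222/1 = 0.2222, so λ = 48 × 0.2222 = 10.67 and power is 83.5%.
- Ratio of noncentralities: 10.67/7.11 = 1.50.

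**Power, group-by-time / adjusted, complete data.**

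| Effect shape | ρ = 0.4 | ρ = 0.5 | ρ = 0.7 |
|---|---|---|---|
| Same on Days 1 and 2 | 58% / 80% | 66% / 84% | 88% / 94% |
| Half on Day 1, full on Day 2 | not tabulated | 53% / 67% | 76% / 83% |
| Day 2 only | not tabulated | 66% / 71% | 88% / 89% |

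At ρ = 0.9 the constant-effect gap is close to zero. To match the adjusted test at 96 per arm, group-by-time needs 143, 131 or 108 per arm (rows in order) at ρ = 0.5, and 119, 113 or 102 at ρ = 0.7. Over a grid of same-direction effects (0.1 to 0.6 SD, ρ from 0.3 to 0.95) the adjusted test was never worse. With opposite-direction effects it lost at most 0.4 points.

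**Main-effect reading.** The estimate is (0 + d + d)/3 = 2d/3, two thirds of a constant effect. Its variance per woman is (1 + 2ρ)/3, or 0.667 at ρ = 0.5. The standardised effect is 0.2222/√(2 × 0.667/96) = 1.89, giving 47% power.

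**Loss of Day 2, group-by-time test, ρ = 0.5 (simulation, 3,000 trials; both loss patterns are assumed).**

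| Effect shape | 20% lost at random: complete-case / mixed model | 70% of women with Day 1 systolic below 140 leave: complete-case / mixed model |
|---|---|---|
| Constant | 55.6% / 62.8% | 43.7% / 61.1% |
| Half on Day 1 | 45.0% / 47.1% | 38.3% / 42.0% |
| Day 2 only | 56.3% / 56.5% | 49.8% / 48.4% |

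**Bias if discharge follows Day 1 pressure.** Assume a true −5 mmHg effect on both days, SD 12, and that women below a Day 1 cut-off leave (10% to 30% of controls, which implies 19% to 46% of treated). Among completers:

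| | ρ = 0.5 | ρ = 0.7 |
|---|---|---|
| Day 2 difference (mmHg) | −4.1 to −3.6 | −3.8 to −3.0 |
| Spurious Day 0 difference (mmHg) | +0.9 to +1.4 | +1.2 to +2.0 |
| Day 1–2 average minus Day 0 (mmHg) | −4.6 to −4.3 | −4.8 to −4.6 |

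**The case against.** The strongest reply is that baseline as a repeated level is a standard, valid design. A constrained longitudinal model also keeps baseline as an outcome and is fully acceptable, so where baseline sits is not the fault in itself. That is right. The loss comes from not using the knowledge that randomised arms share one baseline mean, and the constrained model is an equivalent form of the remedy.

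Second, every power figure rests on assumed values, and the gap narrows as correlation rises. The outcome is a daily mean of up to six readings, and averaging raises day-to-day correlation. If single readings were exchangeable with correlation 0.3 to 0.4, six-reading means would correlate at about 0.72 to 0.80. This stands as a reason to give weight to the ρ = 0.7 column. A Day 0 with few readings would push the other way.

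Third, the SAP's wording points to group-by-time, so the two-thirds dilution belongs to a less likely reading. I agree and do not rest the conclusion on it.

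Fourth, random loss of 20% costs only 0 to 8 points, and in one pressure-dependent scenario complete-case analysis rejects slightly more often. Also true. The better reason for a discharge rule is the distortion among completers.

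Fifth, the protocol does not explicitly schedule a pre-dose reading, and Day#1 in the protocol may not share a clock with Day 1 in the SAP. This supports defining baseline explicitly.

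**Conclusion.** The concern holds. The SAP enters baseline as an outcome level with no adjustment, leaves the treatment test unnamed, and has no rule for discharge before Day 2. With complete data this is an efficiency and specification gap, not a bias. For an assumed 0.33 SD effect at 96 per arm, the loss against a baseline-adjusted joint test is 18 points at correlation 0.5 and 6 at 0.7 if the effect is constant, and 5 and 2 points if it appears only on Day 2. If discharge depends on blood pressure, a complete-case ANOVA also becomes biased. In the illustration above, the −5 mmHg change from baseline shrank by 5% to 14%. The share of women without Day 2 readings is not in the documents.

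The change should be made but is not critical. It concerns a secondary objective, and the primary analysis and sample size are untouched. Confidence is medium, because the size depends on an SD, correlation, effect shape and discharge pattern that the documents do not give.

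**What to change.** For each of the three pressures:

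- Fit a mixed model to the Day 1 and Day 2 daily means with baseline, arm, day and arm-by-day, and an unstructured covariance. A longitudinal model with a common baseline mean is an acceptable equivalent, and it keeps women who lack a baseline reading.
- Define baseline as readings before the first study dose, and state how days are counted.
- Include all randomised women with any post-baseline reading.
- Name the treatment test as the 2-df baseline-adjusted joint test of arm on Days 1 and 2.
- Report each day's difference and the Day 1–2 average with 95% confidence intervals.
- Report, by arm, how many women lack Day 2 readings because of discharge.
- Keep Fisher's exact test as the primary analysis.

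The cost is SAP wording and slightly more programming. No new data are needed, provided pre-dose readings are being recorded. The mixed model assumes data are missing at random given baseline and Day 1 pressure, which is weaker than the assumption behind complete-case ANOVA. The 2-df test gives up some power against a 1-df test of the Day 1–2 average when the effect is constant (84% against 90% at correlation 0.5). If that average is made the single test instead, the SAP should say that it performs poorly when the effect appears mainly on Day 2: 37% power, against 66% for the current group-by-time test.

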- We found four studies investigating loop diuretics in the management of postpartum hypertensive disorders- Matthews et al², Ascarelli et al³, Amorim et al⁴, and Veena et al. Of these studies, only Amorim and Veena were able to show statistical significance on any parameters. Amorim was able to show that there was an improvement of SBP, DBP and MAP, but their research was only presented as an abstract at a conference and not published, thereby making it impossible to draw any conclusions or practice guidelines. Veena demonstrated that by using furosemide and nifedipine in combination, the need for additional antihypertensive medication in severe pre-eclampsia in the postpartum period was reduced when compared to nifedipine alone.
- A systematic review⁵ of postpartum hypertensive disorder management suggested that there was insufficient data to recommend any single pharmacological intervention at this time in the management of gestational hypertensive disorders. The review emphasized the need for further studies to be conducted to help guide management of patients affected by gestational hypertensive disorders in the future.

Objectives

- **Main Question**
 - Does the use of furosemide plus labetalol improve blood pressures in the postpartum period of patients with gestational hypertensive disorders versus labetalol alone?
 - **Primary**
 - Does the addition of a 5-day course of furosemide to labetalol avoid the escalation of anti-hypertensive therapy to control blood pressures.
 - **Secondary:**
 - Does the addition of furosemide to labetalol in postpartum hypertension:
 - Improve of systolic blood pressure, diastolic blood pressure and mean arterial pressure.
 - Shortened hospital stay
 - Affect breastfeeding status at 1 week postpartum visit in mothers planning to breastfeed.
 - Decrease readmission for postpartum hypertensive disorders.

Significance to patient, institution, and profession

- As a busy referral center with a level 3 NICU, Miami Valley care for a large number of patients with gestational hypertensive disorders
- The majority of the OB staff population being served at Miami Valley Hospital is African American. According to Myatt⁶, the incidence of pre-eclampsia in the African American population is greater than double the Caucasian population (11% to 5%) thereby making this study very applicable to our patient population.

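### The only direct blood pressure analysis stops at Day 2, after 2 (or at most 3) of 5 furosemide doses, and the 1-week blood pressure reading is used in no analysis

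*SAP*

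**What the plan says.** The main question, in the protocol's Objectives and again at the head of the SAP, is open-ended in time: "Does the use of furosemide plus labetalol improve blood pressures in the postpartum period of patients with gestational hypertensive disorders versus labetalol alone". The intervention arm receives "a five day course of furosemide 20mg QD on Day#1 or 24 hours after magnesium sulfate" (protocol, Methods), and the primary objective also refers to the 5-day course.

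Pressure itself is analysed in one place, SAP Secondary 1: "Randomization groups will be compared on daily means for each outcome by repeated measures ANOVA". The same sentence fixes the time points, since the aim is to find a "difference in outcomes across time (Day 0/Baseline, Day 1, and Day 2"). The protocol has readings every four hours until discharge. It then states: "The study duration is the length of the hospital stay plus 1 week postpartum blood pressure check". It describes that check as mandatory and lists attendance at it as a potential limitation.

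The protocol's outcome list has highest systolic, highest diastolic and mean arterial pressure, with no time window and no mention of the 1-week reading. In the SAP, the 1-week visit is named only for breastfeeding status.

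**The concern.** The treatment lasts five days, the question covers the postpartum period, and the study runs to a visit whose purpose is to measure blood pressure. The planned pressure analysis nevertheless ends partway through the course and leaves that last reading out.

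Two errors of interpretation follow. A benefit that builds over the later doses would not appear in Secondary 1. An early difference that has gone by the end of the week could be read as an answer to the main question, because nothing later is there to qualify it. In-hospital readings also stop at discharge, and a shorter stay is itself one of the hypothesised effects. The 1-week reading is scheduled for every woman, whenever she goes home.

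**Working it through.** **Plan's own figure.** The protocol Summary gives 96 per group for 8% versus 26%, 90% power, two-sided alpha 0.05. Exact power of the two-sided Fisher test is 0.896 at 94, 0.903 at 96 and 0.909 at 98 per group, so 96 reproduces. This size rests on the primary outcome, and nothing below changes it.

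**Doses covered by the analysis window.** Inputs: one dose a day for five days from Day#1 (protocol, Methods); analysis days 0, 1 and 2 (SAP, Secondary 1). Doses scheduled by the end of day d = d − first dosing day + 1, limited to the range 0 to 5.

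| First dose on | Day 0 | Day 1 | Day 2 | Share of course by Day 2 |
|---|---|---|---|---|
| Day 1 (Day 0 is pre-dose) | 0 | 1 | 2 | 2/5 = 40% |
| Day 0 (Day 0 is a dosing day) | 1 | 2 | 3 | 3/5 = 60% |

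If days are counted from delivery, or magnesium delays the start, the count can be lower. No numbering brings it to five.

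**Where the 1-week check falls.** Assumptions: the first dose is given within the 24-72 h enrolment window, and the check is at 168 h after delivery. The protocol states neither. The fifth daily dose comes 4 × 24 = 96 h after the first.

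- First dose at 24 h: fifth dose at 24 + 96 = 120 h, 48 h before the check.
- First dose at 72 h: fifth dose at 72 + 96 = 168 h, at the time of the check.

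On these assumptions the check falls at or after the last scheduled dose. A later start after magnesium could put it before the last dose.

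**What a 1-week comparison could detect.** Assumptions: systolic SD of 10, 12 or 15 mmHg; either no missed visits (96 per arm) or 20% missed (0.8 × 96 = 76.8, taken as 77). The documents give neither an SD nor an attendance rate. Detectable difference at 90% power = (1.96 + 1.2816) × SD × √(2/n).

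- n = 96: 3.2416 × √(2/96) = 0.468; times 10, 12, 15 gives 4.7, 5.6, 7.0 mmHg.
- n = 77: 3.2416 × √(2/77) = 0.522; times 10, 12, 15 gives 5.2, 6.3, 7.8 mmHg.

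The formula takes no credit for adjustment for the pre-treatment value, which would lower these figures to the extent that the two readings are correlated.

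**The case against.** A reader might infer that the main question goes untested beyond the first doses, or that the trial as a whole can speak only to one or two doses. The documents do not support that. The primary and secondary objectives are nested under the main question. The primary analysis counts any labetalol increase over the whole hospital stay, and the readmission analysis covers time after discharge. The gap is in one secondary analysis. Still, neither of those outcomes is a pressure measurement, and the primary does not see any part of the course taken at home.

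A reader might also take 2 of 5 doses as established. It is not, because Day 0 is undefined and 3 of 5 is possible. Nor can one say that the protocol excludes the 1-week reading from its outcomes: their window is simply unstated. The restriction to Day 2 is the SAP's.

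There is a fair case for early, frequent, supervised readings as the main pressure comparison. A single clinic reading is a different measure from a daily average. Labetalol is titrated to a common target in both arms, so by one week any difference may have narrowed, and some women will not attend. These points limit how a 1-week comparison is interpreted. They do not make the Day 0-2 analysis informative about the end of the course, and titration affects Days 1 and 2 as well.

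Finally, the documents give no length of stay, so the share of women with in-hospital readings after Day 2 is unknown. Whatever that share is, Secondary 1 does not use those readings.

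**Conclusion.** The point holds for Secondary 1. Its window covers 40% of the scheduled course, or 60% if Day 0 is a dosing day, and under no numbering does a pressure analysis reach the fifth dose. The 1-week reading, already scheduled as the end of study, is named in no outcome and enters no analysis. As planned, Secondary 1 supports a statement about early in-hospital pressure and nothing later.

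The primary analysis and the sample size are unaffected, so this is an improvement that should be made rather than a flaw that undermines the trial. The dose count needs only the stated once-daily schedule and a convention for Day 0. The placement of the check relative to the last dose and the detectable difference of about 5-8 mmHg rest on assumed timings, SD and attendance. The documents give no expected pressure effect against which to judge that difference.

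**What to change.** - Define Day 0 in the SAP relative to the first study dose, and tie the SAP days to the protocol's Day#1.
- Add to SAP Secondary 1 a pre-specified between-arm comparison of systolic, diastolic and mean arterial pressure at the 1-week check, adjusted for the pre-treatment value (for example by ANCOVA). Name that reading in the protocol's outcome list.
- Report the visit date, the date of the last furosemide dose and the current labetalol dose descriptively by arm. Do not adjust the comparison for labetalol dose, which is a post-randomisation variable.
- Report attendance by arm and state a missing-data rule in advance.
- Describe the Day 1-2 result as an early in-hospital effect.

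The visit already takes place, so the cost is SAP and protocol wording, a few extra data fields and three more secondary tests. Some visits will be missed, some may fall before the fifth dose, and titration may narrow the differences. The report should say so.

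### Length of stay is compared by an unadjusted t-test, although cesarean delivery and time from delivery to entry could be used as covariates; the test is unbiased, and adjusting is an optional gain in precision of unknown size

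*SAP*

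**What the plan says.** SAP, Secondary 2, gives one sentence on the analysis: "Randomization groups will be compared on hospital length of stay using a Student T-test". The Protocol Summary is no more specific for this type of outcome: "Student T-Test and Mann Whitney U tests will be utilized to compare continuous variables". Neither document plans a covariate-adjusted analysis of stay.

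The Protocol's list of outcome variables (Methods) has the item as "Length of postpartum stay (days", with days as the unit. The SAP speaks only of hospital stay. Neither document says when the clock starts or stops, or whether days are rounded.

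Two other entries in Protocol, Methods, matter here. The inclusion criteria admit patients at "Postpartum: 24-72 hours after delivery", a window 48 hours wide. The demographics list includes "Cesarean delivery (yes, no", but no planned analysis uses it. The interval from delivery to randomisation is not a listed variable. The design is a "prospective, randomized 1:1 controlled study", and no stratification factor is stated.

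**The concern.** Shorter stay is a stated secondary objective. A two-sample t-test puts all between-patient variation in stay into the error term, including variation from factors already fixed when the patient is randomised. Two such factors can be seen in the plan.

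- **Mode of delivery.** Stay may differ between cesarean and vaginal births.
- **Time of entry.** Discharge follows enrolment, so entry time sets a floor under the postpartum stay, and some positive association is to be expected. Only the 48-hour spread of entry times adds variance. The delay shared by all patients does not.

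If these factors matter, a model containing them gives a narrower confidence interval for the arm difference from the same patients. What is at stake is the chance of detecting a modest saving in stay. The validity of the comparison is not in question.

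**Working it through.** **The plan's own figure.** The only sample-size figure is 96 per group, for the primary outcome: "Based on an estimated 8% need for increase in anti-hypertensive medication in the furosemide group and a 26% need in the standard treatment arm", with 90% power and two-sided alpha 0.05. Enumerating the two-sided Fisher's exact test gives 89.9% power at 95 per group and 90.3% at 96, so the figure reproduces. It says nothing about stay, for which the documents give no SD, target difference or power.

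**From the documents:** n = 96 per arm; two-sided alpha 0.05 (stated for the primary, used here); entry window 24 to 72 hours, width 2 days.

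**Assumed:**
- total SD of stay: 1, 1.5, 2 or 3 days
- entry time uniform over the window and independent of mode of delivery
- b, the days of extra stay per day of later entry: 0.25 (low case) or 1 (high case)
- cesarean share p: 30% (low) or 50% (high)
- cesarean effect d: 0.5 day (low) or 1 day (high)

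**Step 1: variance explained.**
Var(entry time) = 2²/12 = 0.333 day², SD 0.58 day.
Explained variance = b² × 0.333 + p(1−p)d².
- Low: 0.0625 × 0.333 + 0.21 × 0.25 = 0.0208 + 0.0525 = 0.0733 day²
- High: 1 × 0.333 + 0.25 × 1 = 0.583 day²

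The share removed is R² = explained variance / SD².

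**Step 2: detectable difference and power.** With 80% power the unadjusted test detects 2.80 × √(2/96) = 0.404 SD. Adjustment multiplies this by √(1−R²). For example, at SD 1 day, 0.404 × 24 = 9.7 h, and 9.7 × √(1−0.583) = 6.3 h.

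| SD (days) | R², low / high | Detectable difference: unadjusted → low / high | Power for 0.5 day: unadjusted → low / high |
|---|---|---|---|
| 1 | 7% / 58% | 9.7 h → 9.3 / 6.3 h | 93% → 95% / >99% |
| 1.5 | 3% / 26% | 14.6 h → 14.3 / 12.5 h | 64% → 65% / 77% |
| 2 | 2% / 15% | 19.4 h → 19.2 / 17.9 h | 41% → 42% / 47% |
| 3 | 1% / 6.5% | 29.1 h → 29.0 / 28.2 h | 21.0% → 21.2% / 22.2% |

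**Step 3: cesarean alone.** This is the covariate already collected. It explains 0.0525 to 0.25 day², which is 5% to 25% of the variance at SD 1 day and 0.6% to 2.8% at SD 3 days.

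**Step 4: the clock.** Let T be the time from delivery to randomisation, L stay counted from delivery, and L − T stay counted from randomisation. If L is regressed on arm, cesarean and T, then regressing L − T on the same terms changes only the coefficient of T, which falls by 1. The arm coefficient and the residuals are identical.

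Moving the clock without the covariate is a different matter: Var(L − T) = SD² + 0.333 − 2b × 0.333, which is below SD² only if b > 0.5. At b = 0 it is 33% higher at SD 1 day and 8% higher at SD 2 days. The covariate therefore does the work, and the choice between these two clocks does not.

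**The case against.** **The t-test is legitimate.** Randomisation makes the unadjusted comparison unbiased. Stay is a secondary outcome with no stated power, and the trial was sized on escalation of treatment. Choosing an adjusted model is a preference for efficiency. This stands in full and sets the severity.

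**The gain may be negligible.** If discharge tracks time since delivery rather than time since entry, b is near zero and the entry window contributes almost nothing. Uniform entry is also unsupported, because Protocol, Methods, ties the start of treatment to Day 1 or to an interval after magnesium sulfate. This stands too, and it is why the lower end of the range is about 1%.

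**A stronger reading is tempting.** A reader might infer that stay is counted in whole days from delivery and that a large share of its variance is avoidable. Take a residual SD of 24 h (576 h²), a full entry-window term (48²/12 = 192 h²), a 24 h cesarean effect at 30–50% share (121–144 h²) and a rounding term (24²/12 = 48 h²). The total is 937–960 h², of which all but the residual, 38–40%, appears removable. The documents do not support this, for three reasons:
- Neither document defines the start of the clock or says that days are whole, so the rounding term is supposition.
- No covariate removes rounding. On the same inputs the covariates remove 313/937 = 33% to 336/960 = 35%, and the detectable difference becomes 2.80 × √(2 × 624/96) = 10.1 h.
- Entering the full 192 h² sets b = 1, and nothing in the documents fixes that slope.

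**The data may not be to hand.** The interval from delivery to randomisation is not a listed variable, and REDCap is named only for randomisation. This stands as a small cost. Eligibility cannot be checked without knowing the time since delivery, so the information should exist in the chart.

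**Conclusion.** The point holds as an optional, low-cost improvement. Three facts rest on the documents: the test is unadjusted, cesarean status is recorded but unused in any analysis, and entry varies over a 48-hour window. That adjustment would help materially does not rest on them. Under the stated assumptions the share of variance removed is about 1% to 58%. It is large only if the SD of stay is about 1 to 1.5 days and both factors act strongly. At an SD of 2 to 3 days, power for a half-day difference rises by at most about 6 percentage points. The range illustrates these inputs and is not a bound; a cesarean effect above 1 day, for instance, would raise it.

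The t-test should not be read as biased or invalid. Separately, the undefined start and stop should be settled whichever test is used, since two analysts could otherwise compute different stays from the same chart.

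**What to change.** In SAP, Secondary 2:

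1. State when stay starts and stops, and record it in hours where timestamps allow.
2. Replace the t-test by a prespecified linear model of stay on arm, cesarean delivery (yes/no) and hours from delivery to randomisation. Report the arm coefficient with its confidence interval.
3. Count stay from delivery or from randomisation. With the interval in the model and the same stop time, both give the same arm estimate. This equivalence does not extend to a clock that starts at admission.
4. If the times cannot be extracted for all patients, adjusting for cesarean delivery alone needs no new data.

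The cost is SAP wording, extraction of delivery and randomisation times (and discharge times where hours are used), and two degrees of freedom (190 to 188 with 192 patients). An adjusted mean difference is slightly less simple to report than two raw means, which can still be shown beside it.
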